8.4.2 Vital signs

Vital signs will include the collection of oral body temperature (recorded in °C), blood pressure (BP) and pulse measurements.

After the patient has been sitting for 5 minutes, with back supported and both feet placed on the floor, systolic and diastolic BP will be measured using an automated validated device, e.g., OMRON with an appropriately sized cuff. In case the cuff sizes available are not large enough for the patient's arm circumference, a sphygmomanometer with an appropriately sized cuff may be used.

Body temperature will be monitored as indicated in the study assessment schedule table (Table 8-1) and recorded on the clinical database. Fever monitoring will be done every 6 hours until resolution of fever, defined as being afebrile for 24 hours.

If vital signs are out-of-range at screening (see Exclusion Criteria Section 5.2 of the protocol for details), two additional readings can be obtained, so that a total of three consecutive assessments are made, with the patient seated quietly for approximately five minutes preceding each repeat assessment. The last reading must be within the ranges provided in the eligibility criteria in order for the patient to qualify.

In case of repeated vital sign assessments, the eCRF should contain the qualifying results.

8.4.3 Electrocardiograms

Electrocardiograms (ECGs) must be recorded after 10 minutes rest in the supine position to ensure a stable baseline. The preferred sequence of cardiovascular data collection during study visits is ECG collection first, followed by vital signs, blood sampling, and any remaining assessments for that visit (refer to flow diagram below).

Figure 8-1 **Timing of study procedures**

CCI

8.4.4 Clinical safety laboratory tests

As per [Section 4.6](#), during a public health emergency as declared by local or regional authorities' i.e., pandemic, epidemic or natural disaster, that limits or prevents on-site study visits, if patients cannot visit the site for protocol-specified safety lab assessments, an alternative lab (local) collection site may be used.

Clinically significant abnormalities must be recorded as either medical history/current medical conditions or adverse events as appropriate.

In the case where a laboratory range is not specified by the protocol, but a value is outside the reference range for the laboratory at screening, a decision regarding whether the result is of clinical significance or not shall be made by the investigator (in consultation with the Sponsor) and shall be based, in part, upon the nature and degree of the observed abnormality. The assessment may be repeated once prior to randomization.

All abnormal lab results must be evaluated for criteria defining the inclusion/exclusion criteria, an adverse event and reported as such if the criteria are met. For those lab adverse events, repeated evaluations are mandatory until normalization of the result(s) or until the result is no longer considered to be clinically significant.

In all cases, the investigator must document in the source documents, the clinical considerations (i.e., result was/was not clinically significant and/or medically relevant) in allowing or disallowing the patient to continue in the study.

Local laboratories will be used for analysis of safety specimens.

Urinalysis

A midstream urine sample (approx. 30 mL) will be obtained, in order to avoid contamination with epithelial cells and sediments, and allow proper assessments.

Special clinical laboratory evaluations

All abnormal lab results must be evaluated for criteria defining an adverse event and reported as such if the criteria are met. For those lab adverse events, repeated evaluations are mandatory until normalization of the result(s) or until the result is no longer considered to be clinically significant.

Table 8-2 Laboratory assessments

The CCI logo is displayed in red text on a black rectangular background.

8.4.5 Pregnancy testing

Condom use is required for all sexually active male patients to prevent them from fathering a child AND to prevent delivery of study treatment via seminal fluid to their partner. In addition, male patients should not donate sperm for the time period specified above.

All pre-menopausal women who are not surgically sterile will have pregnancy testing. Additional pregnancy testing might be performed if requested by local requirements.

A serum or plasma pregnancy test will be performed at the screening visit and/or pre-dose and urine pregnancy test will be performed at study completion. All female patients in this study must undergo obligatory pregnancy testing as per schedule of assessment. Local pregnancy test and associated results will not be collected on CRF.

Assessments of fertility

A woman is considered of childbearing potential from menarche and until becoming post-menopausal unless permanently sterile. Permanent sterilization methods include hysterectomy, bilateral salpingectomy and bilateral oophorectomy. Medical documentation of oophorectomy, hysterectomy, or tubal ligation must be retained as source documents.

A post-menopausal state is defined as no menses for 12 months without an alternative medical cause and an appropriate clinical profile.

In absence of the medical documentation confirming permanent sterilization, or if the post-menopausal status is not clear, the investigator should use his medical judgment to appropriately evaluate the fertility state of the woman and document it in the source document.

8.4.6 Other safety evaluations

Signs and symptoms of severe malaria

Danger signs:

- not able to drink
- vomiting > twice within preceding 24 hours
- one convulsion within preceding 24 hours
- unconscious state
- unable to sit or stand

Signs of severe malaria:

Severe *P. falciparum* malaria is defined as one or more of the following, occurring in the absence of an identified alternative cause and in the presence of *P. falciparum* asexual parasitemia:

- Impaired consciousness (Glasgow coma score < 11 in adults)
- Prostration (generalized weakness i.e., unable to sit, stand or walk without assistance)
- Multiple convulsions (more than two episodes within 24 hours)
- Acidosis (a base deficit of > 8 mEq/L or if not available a plasma bicarbonate level of < 15 mmol/L or venous plasma lactate \geq 5 mmol/L. Severe acidosis manifests clinically as respiratory distress i.e., rapid, deep, labored breathing)
- Hypoglycemia (blood or plasma glucose < 2.2 mmol/L; < 40 mg/dL)
- Severe malarial anemia (hemoglobin concentration \leq 5 g/dL or a hematocrit of \leq 15% in children < 12 years of age (< 7 g/dL and < 20% respectively in adults) with a parasite count > 10,000/ μ L)
- Renal impairment (plasma or serum creatinine > 265 μ mol/L (3 mg/dL) or blood urea > 20 mmol/L)
- Jaundice (plasma or serum bilirubin > 50 μ mol/L (3 mg/dL) with a parasite count > 100,000/ μ L)
- Pulmonary edema (radiologically confirmed or oxygen saturation < 92% on room air with a respiration rate > 30/min, often with chest indrawing and crepitation on auscultation)
- Significant bleeding (including recurrent or prolonged bleeding from the nose, gums of venipuncture sites, hematemesis or melena)
- Shock (compensated shock i.e., capillary refill \geq 3s or temperature gradient on leg but no hypotension; decompensated shock i.e., systolic blood pressure < 70 mm Hg in children or < 80 mm Hg in adults with evidence of impaired perfusion)
- Hyperparasitemia (*P. falciparum* parasitemia > 10%)

If a patient experiences and danger signs / signs of severe malaria, the investigator should report the event as an SAE following the guidance provided in [Section 8.6.3](#). Local guidance should be followed for the treatment of these danger signs / signs of severe malaria.

8.4.7 Appropriateness of safety measurements

The safety assessments selected are standard for this indication/patient population.

8.5 Additional assessments

As per [Section 4.6](#), during a public health emergency as declared by local or regional authorities' i.e., pandemic, epidemic or natural disaster, that limits or prevents on-site study visits, if patients cannot visit the site for protocol-specified PK and CCI, an alternative lab (local) collection site may be used.

8.5.1 Meal Records

Meal records are required for domiciled meals on the day(s) indicated in the assessment table (Table 8-1).

For domiciled meals on days indicated in the Assessment Schedule Table 8-1, the date and start and end time and percentage of meal consumption will be recorded in the appropriate section of the eCRFs.

8.5.2 Other assessments

CCI

8.6 Adverse events (AEs), serious adverse events (SAEs), and other safety reporting

The definitions of adverse events (AEs) and serious adverse events (SAEs) can be found in Section 8.6.2.

AEs will be reported by the patient (or, when appropriate, by a caregiver, surrogate, or the patient's legally authorized representative).

The investigator and any qualified designees are responsible for detecting, documenting, and recording events that meet the definition of an AE or SAE and remain responsible for following up all AEs (see Section 7).

The method of recording, evaluating, and assessing causality of AEs and SAEs and the procedures for completing and transmitting SAE reports are provided in Section 8.6.3.

8.6.1 Adverse events

An adverse event (AE) is any untoward medical occurrence (e.g., any unfavorable and unintended sign [including abnormal laboratory findings], symptom or disease) in a clinical investigation patient after providing written informed consent for participation in the study. Therefore, an AE may or may not be temporally or causally associated with the use of a medicinal (investigational) product.

The occurrence of adverse events must be sought by non-directive questioning of the patient at each visit during the study. Adverse events also may be detected when they are volunteered by the patient during or between visits or through physical examination findings, laboratory test findings, or other assessments.

Adverse events must be recorded under the signs, symptoms, or diagnosis associated with them, accompanied by the following information (as far as possible) (if the event is serious refer to Section 8.6.2):

1. The severity grade

- mild: usually transient in nature and generally not interfering with normal activities
- moderate: sufficiently discomforting to interfere with normal activities
- severe: prevents normal activities

2. Its relationship to the study treatment and other investigational treatment. If the event is due to lack of efficacy or progression of underlying illness (i.e., progression of the study indication) the assessment of causality will usually be 'Not suspected.' The rationale for this guidance is that the symptoms of a lack of efficacy or progression of underlying illness are not caused by the trial drug, they happen in spite of its administration and/or both lack of efficacy and progression of underlying disease can only be evaluated meaningfully by an analysis of cohorts, not on a single patient
3. Its duration (start and end dates or ongoing) and the outcome must be reported
4. Whether it constitutes a SAE (see [Section 8.6.2](#) for definition of SAE) and which seriousness criteria have been met
5. Action taken regarding with study treatment.

All adverse events must be treated appropriately. Treatment may include one or more of the following:

- Dose not changed
- Dose Reduced/increased
- Drug interrupted/permanently discontinued

6. Its outcome

Conditions that were already present at the time of informed consent should be recorded in medical history of the patient.

Adverse events (including lab abnormalities that constitute AEs) should be described using a diagnosis whenever possible, rather than individual underlying signs and symptoms.

Adverse event monitoring should be continued for at least 30 days (or 5 half-lives or end of study visit, whichever is longer) following the last dose of study treatment.

Once an adverse event is detected, it must be followed until its resolution or until it is judged to be not recovered/not resolved (e.g., continuing at the end of the study), and assessment must be made at each visit (or more frequently, if necessary) of any changes in severity, the suspected relationship to the interventions required to treat it, and the outcome.

Information about adverse drug reactions for the investigational drug can be found in the Investigator's Brochure (IB).

Abnormal laboratory values or test results constitute adverse events only if they fulfill at least one of the following criteria:

- they induce clinical signs or symptoms
- they are considered clinically significant
- they require therapy

Clinically significant abnormal laboratory values or test results must be identified through a review of values outside of normal ranges/clinically notable ranges, significant changes from baseline or the previous visit, or values which are considered to be non-typical in patient with uncomplicated malaria.

8.6.2 Serious adverse events

An SAE is defined as any adverse event [appearance of (or worsening of any pre-existing)] undesirable sign(s), symptom(s), or medical condition(s) which meets any one of the following criteria:

- fatal
- life-threatening

Life-threatening in the context of a SAE refers to a reaction in which the patient was at risk of death at the time of the reaction; it does not refer to a reaction that hypothetically might have caused death if it were more severe (please refer to the ICH-E2D Guidelines).

- results in persistent or significant disability/incapacity
- constitutes a congenital anomaly/birth defect, fetal death or a congenital abnormality or birth defect
- requires inpatient hospitalization or prolongation of existing hospitalization, unless hospitalization is for:
 - routine treatment or monitoring of the studied indication, not associated with any deterioration in condition
 - elective or pre-planned treatment for a pre-existing condition that is unrelated to the indication under study and has not worsened since signing the informed consent
 - social reasons and respite care in the absence of any deterioration in the patient's general condition
 - treatment on an emergency outpatient basis for an event not fulfilling any of the definitions of a SAE given above and not resulting in hospital admission
- is medically significant, e.g., defined as an event that jeopardizes the patient or may require medical or surgical intervention to prevent one of the outcomes listed above

Medical and scientific judgment should be exercised in deciding whether other situations should be considered serious reactions, such as important medical events that might not be immediately life-threatening or result in death or hospitalization but might jeopardize the patient or might require intervention to prevent one of the other outcomes listed above. Such events should be considered as “medically significant.” Examples of such events are intensive treatment in an emergency room or at home for allergic bronchospasm, blood dyscrasias, or convulsions that do not result in hospitalization or development of dependency or abuse (please refer to the ICH-E2D Guidelines).

All new malignant neoplasms will be assessed as serious under “medically significant” if other seriousness criteria are not met and the malignant neoplasm is not a disease progression of the study indication.

All reports of intentional misuse and abuse of the product are also considered serious adverse events irrespective of whether a clinical event has occurred.

Any suspected transmission via a medicinal product of an infectious agent is also considered a serious adverse reaction.

8.6.3 SAE reporting

To ensure patient safety, every SAE, regardless of causality, occurring after the patient has provided informed consent and until 30 days following the last administration of study treatment if there are post-treatment follow-up visits with no required procedures must be reported to Novartis safety immediately, without undue delay, but under no circumstances later than within 24 hours of obtaining knowledge of the events (Note: If more stringent, local regulations regarding reporting timelines prevail). Detailed instructions regarding the submission process and requirements are to be found in the investigator folder provided to each site. Information about all SAEs is collected and recorded on the Serious Adverse Event Report Form; all applicable sections of the form must be completed in order to provide a clinically thorough report.

SAEs occurring after the patient has provided informed consent until the time the patient is deemed a Screen Failure must be reported to Novartis.

All follow-up information for the SAE including information on complications, progression of the initial SAE and recurrent episodes must be reported as follow-up to the original episode immediately, without undue delay, but under no circumstances later than within 24 hours of the investigator receiving the follow-up information (Note: If more stringent, local regulations regarding reporting timelines prevail). An SAE occurring at a different time interval or otherwise considered completely unrelated to a previously reported one must be reported separately as a new event.

If the SAE is not previously documented in the Investigator's Brochure or Package Insert (new occurrence) and is thought to be related to the study treatment, a CMO & PS Department associate may urgently require further information from the investigator for health authority reporting. Novartis may need to issue an Investigator Notification (IN) to inform all investigators involved in any study with the same study treatment that this SAE has been reported.

Suspected Unexpected Serious Adverse Reactions (SUSARs) and SAEs will be collected and reported to the competent authorities and relevant ethics committees in accordance with EU Guidance 2011/C 172/01 or as per national regulatory requirements in participating countries.

Any SAEs experienced after the 30-day period following the last administration of study treatment should only be reported to Novartis Safety if the investigator suspects a causal relationship to study treatment, unless otherwise specified by local law/regulations.

Protocol specific SAEs to be reported to Novartis within 24 hrs:

The logo consists of the letters 'CCI' in a bold, red, sans-serif font. The letters are positioned on the left side of a solid black rectangular background that spans the width of the page.

8.6.4 Pregnancy Reporting

- Details of all pregnancies in female patients and, if indicated, female partners of male patients will be collected after the start of study treatment and until 30 days after administration of study drug or for 5 half-lives, whichever is longer.
- While pregnancy itself is not considered to be an AE or SAE, any pregnancy complication or elective termination of a pregnancy for medical reasons will be reported as an AE or SAE.
- Abnormal pregnancy outcomes (e.g., spontaneous abortion, fetal death, stillbirth, congenital anomalies, ectopic pregnancy) are considered SAEs and will be reported as such.
- Any post study pregnancy-related SAE considered reasonably related to the study treatment by the investigator will be reported to Novartis as described in [Section 8.6.3](#). While the investigator is not obligated to actively seek this information in former study patients/pregnant female partners, he or she may learn of an SAE through spontaneous reporting.

Any female patient who becomes pregnant while participating in the study will discontinue the study.

Pregnancies

If a female trial patient becomes pregnant, the study treatment should be stopped, and the pregnancy consent form should be presented to the trial patient. The patient must be given adequate time to read, review and sign the pregnancy consent form. This consent form is necessary to allow the investigator to collect and report information regarding the pregnancy. To ensure patient safety, each pregnancy occurring after signing the informed consent must be reported to Novartis within 24 hours of learning of its occurrence. The pregnancy should be followed up to determine outcome, including spontaneous or voluntary termination, details of the birth, and the presence or absence of any birth defects, congenital abnormalities, or maternal and/or newborn complications.

Pregnancy should be recorded and reported by the investigator to the Novartis Chief Medical Office and Patient Safety (CMO&PS). Pregnancy follow-up should be recorded on the same form and should include an assessment of the possible relationship to the investigational medicinal product in any pregnancy outcome. Any SAE experienced during pregnancy must be reported.

If a female partner of a male trial patient who took study treatment in this study becomes pregnant, pregnancy outcomes should be collected. Consent to report information regarding these pregnancy outcomes should be obtained from the mother.

After consent is provided, the pregnancy reporting will occur up to one year after the estimated date of delivery.

8.6.5 Disease-related events and/or disease-related outcomes not qualifying as AEs or SAEs

There are no disease-related events and/or disease-related outcomes that would not qualify as an AE or SAE.

8.7 Pharmacokinetics

PK samples will be collected at the visits defined in the cohort specific assessment schedules ([Section 12](#)). Follow instructions outlined in the laboratory manual regarding sample collection, numbering, processing and shipment. CCI

In order to better define the PK profile, the timing of the PK sample collection may be altered based on emergent data. Pharmacokinetic (PK) samples will be obtained and evaluated in all patients treated with the anti-malarial agents and combinations included in this study at all dose levels. A bioanalyst will only analyze samples from the patients on investigational drug(s). The parent drug(s) will be determined by a validated LC-MS/MS method. CCI

Concentrations will be expressed in mass per volume units and will refer to the free base. Concentrations below the LLOQ will be reported as “zero” and missing data will be labeled as such in the Bioanalytical Data Report. In case of missing drug concentrations, impact of this on PK parameter calculation and interpretation will be considered.

For standard pharmacokinetic abbreviations and definitions, see the [List of Abbreviations](#).

The following pharmacokinetic parameters will be determined using the actual recorded sampling times and non-compartmental method(s) with Phoenix WinNonlin (Version 6.4 or higher): C_{max}, T_{max}, AUC_{last}, AUC_{inf}, T_{1/2}, V_z/F and CL/F from the plasma concentration-time data.

The linear trapezoidal rule will be used for AUC calculation. Regression analysis of the terminal plasma elimination phase for the determination of T_{1/2} will include at least 3 data points after C_{max}. If the adjusted R² value of the regression analysis of the terminal phase will be less than 0.75, no values will be reported for T_{1/2}, AUC_{inf} and CL/F.

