12.3.8 Cohort B2 PK/PD and Biomarker Assessments

CCI

CCI

Pharmacokinetic assessments will be performed as described in [Section 8.7](#). In addition to PK parameters mentioned in [Section 8.7](#), C_{168h} (concentration at 168h) and AUC_{0-168h} (Area under the plasma concentration time curve from zero to 168h) will be determined using the actual recorded sampling times and non-compartmental method(s) with Phoenix WinNonlin (Version 6.4 or higher).

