## 2.8 Pharmacokinetic endpoints

The PK analysis set will be used for the pharmacokinetics analyses.

PK parameters in [Table 2-5](#) will be determined using the actual recorded sampling times and non-compartmental method(s) with Phoenix WinNonlin (Version 6.4 or higher). If  $R_{sq\_adj} < 0.75$  or  $AUC\%_{Extrap} > 20\%$ , then  $\lambda_z$ ,  $T_{1/2}$ ,  $AUC_{inf}$ ,  $V_z/F$ ,  $CL/F$  will be flagged for exclusion.

Drug concentrations below the lower limit of quantitation (LLOQ) will be set to zero by the Bioanalyst and will be displayed in the listings as zero and flagged. Below LLOQ values will be treated as missing for the calculation of the geometric means and geometric CV%, and as zero for all other calculations including calculation of PK parameters.

CCI

AUClast	The AUC from time zero to the last measurable concentration sampling time (tlast) (mass x time x volume  )
AUCinf	The AUC from time zero to infinity (mass x time x volume  )
Cmax	The maximum (peak) observed plasma, blood, serum, or other body fluid drug concentration after single dose administration (mass x volume  )
Tmax	The time to reach maximum (peak) plasma, blood, serum, or other body fluid drug concentration after single dose administration (time)
Lambda_z	Smallest (slowest) disposition (hybrid) rate constant (time  ) may also be used for terminal elimination rate constant (time  )
T1/2	The elimination half-life associated with the terminal slope (λz) of a semi logarithmic concentration-time curve (time). Use qualifier for other half-lives
CL/F	The total body clearance of drug from the plasma (volume x time  )
Vz/F	The apparent volume of distribution during terminal phase (associated with λz) (volume)

[illegible][illegible]

CCI

CCI

CCI

- PK parameters with efficacy outcomes CCI related to parasite dynamics, cure, and protein levels CCI wherever applicable

See [Section 2.9](#).

- Presence of gametocytes at baseline (pre-dose) and post-treatment, respectively

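### Protocol 8.7 computes AUC with the plain linear trapezoidal rule, which can overstate AUC and understate CL/F where elimination-phase samples are a half-life or more apart

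*Protocol*

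**What the plan says.** Protocol 8.7 gives the integration rule in one unqualified sentence: "The linear trapezoidal rule will be used for AUC calculation". AUC is derived by non-compartmental analysis in Phoenix WinNonlin from actual sampling times. The same section says that "PK samples will be collected at the visits defined in the cohort specific assessment schedules" and that "the timing of the PK sample collection may be altered based on emergent data". Those schedules, in Section 12, are redacted. If concentrations are missing, 8.7 says that the effect on parameter calculation will be considered, without saying how.

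Protocol 12.3.8 adds two Cohort B2 parameters, the concentration at 168 h and the "Area under the plasma concentration time curve from zero to 168h".

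SAP 2.8 repeats the non-compartmental method and flags lambda_z, T1/2, AUCinf, Vz/F and CL/F for exclusion if adjusted R-squared is below 0.75 or more than 20% of AUC is extrapolated. Its visible text gives no trapezoidal rule; part of the section is redacted.

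PK is a secondary objective in Protocol Table 2-1. Protocol 1.1 says that PK will inform dose selection for future studies. Protocol 3.1 and 4.4 allow Part B doses to be adjusted towards a desired exposure after about 6 patients per arm.

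**The concern.** A straight line between two points on an exponential decline lies above the curve, so the linear rule overstates the area of every such interval. The excess depends only on the interval divided by the half-life. CL/F is dose divided by AUCinf, so it falls as AUCinf rises, and Vz/F falls with it.

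The error depends on the sampling grid, and the grid can vary between patients and cohorts: schedules are cohort-specific, timing may be changed, and samples may be missed. A missed sample joins two intervals into one and enlarges the error, so a gap in sampling can look like higher exposure. The two exclusion flags in SAP 2.8 test the terminal fit and the extrapolated share; neither detects this. The effect of one incomplete profile is greatest in a summary of about 6 patients.

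**Working it through.** The documents give no AUC or bias figure to reproduce. The check has three steps.

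**1. One declining interval.** For an interval of length τ and rate constant k = ln2 / half-life, starting at concentration C0:

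- linear area = τ · C0 · (1 + e^(−kτ)) / 2
- true area = C0 · (1 − e^(−kτ)) / k
- ratio = (kτ/2) · coth(kτ/2)

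| τ in half-lives | linear / (τC0) | true / (τC0) | excess |
|---|---|---|---|
| 0.5 | 0.8536 | 0.8451 | +1.0% |
| 1 | 0.7500 | 0.7213 | +4.0% |
| 2 | 0.6250 | 0.5410 | +15.5% |

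This step needs no assumption beyond exponential decline.

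**2. What the documents show about spacing.** Two items bear on it.

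- 168 h is a named PK time in Cohort B2 (Protocol 12.3.8).
- SAP 5.1.3 gives the example of a Day 4 visit that takes place on Day 7 and is mapped to Day 8. Its rule sets a window's upper limit at the target day plus the integer part of half the distance to the next visit. With Day 8 next, the Day 4 window ends at 4 + (8 − 4)/2 = Day 6, so Day 7 maps to Day 8, as in the example. An applicable visit on Day 6 would have captured Day 7 (6 + (8 − 6)/2 = 7), and so would one on Day 7. A Day 5 visit is not strictly excluded (5 + integer part of 3/2 = 6).

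The example therefore suggests a Day 4 to Day 8 gap, about 72 h to 168 h, for the assessments it covers. It does not prove that PK is among them.

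**3. Whole profile, on assumed inputs.** One-compartment oral model with concentration proportional to e^(−kt) − e^(−ka·t), ka = 0.5/h, half-life 24 to 144 h. Base grid: 0, 1, 2, 4, 6, 8, 12, 24, 48, 72, 168, 360 h. The grid, ka and half-lives are all assumptions. Error of the linear rule against the exact integral:

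| Grid and range | 24 h | 48 h | 72 h | 96 h | 144 h |
|---|---|---|---|---|---|
| Base, 0-168 h | +8.7% | +4.9% | +2.8% | +1.7% | +0.8% |
| Base, 0-360 h | +10.1% | +9.4% | +7.0% | +5.1% | +2.9% |
| Base plus 96, 264 h; 0-360 h | +4.2% | +3.2% | +2.2% | +1.5% | +0.8% |
| Base plus 36, 96, 120, 240 h; 0-360 h | +1.8% | +1.8% | +1.5% | +1.1% | +0.7% |
| Base without 72 h, 0-168 h | +22.9% | +11.2% | +6.0% | +3.6% | +1.7% |

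(Columns are half-lives.) In every cell the linear-up/log-down error is between −0.3% and zero.

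For AUCinf = AUClast + Clast/λz on the base grid to 360 h, with the true λz, the error runs from +10.1% (24 h) to +2.3% (144 h). The extrapolated tail dilutes the excess only slightly. CL/F changes by 1/1.101 − 1 = −9.2% to 1/1.023 − 1 = −2.2%.

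**Two stress cases**, with half-lives of 12 to 168 h and absorption half-lives of 0.7 or 2 h:

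- A much sparser grid (0, 4, 8, 24, 72, 168, 672 h) gave AUCinf errors of +4.1% to +28.1%; linear-up/log-down gave −6.4% to −0.3%.
- Sparse early and dense late sampling (first post-dose sample at 6 h) gave −9.5% to +1.0% with the linear rule and −12.0% to −0.4% with linear-up/log-down.

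**The case against.** The strongest reply is that this is a choice between two accepted non-compartmental options, that the choice was prespecified, and that its effect here is unknown. The PK schedule is redacted, and adding four samples to the assumed grid brings the error down to 0.7-1.8%. Where the peak is poorly sampled, the linear excess partly cancels an unrelated loss, and log-down moves the total further from the truth. PK is secondary, and only investigational-drug samples are assayed, so no PK comparison with Coartem is affected. The SAP follows protocol version 03 of 20-Mar-2024, while the latest amendment listed in the supplied protocol is from June 2023, so the rule now in force cannot be confirmed.

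Most of this stands, and it keeps the point small and conditional. The cancellation is not a defence: missing the peak is a separate sampling problem, and offsetting it with a decline-phase error would be luck. The version gap is a further reason to state the rule in the SAP.

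Three stronger readings are tempting, and the documents do not support them.

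- A reader might infer sparse PK sampling from the 168 h, 360 h and end-of-study samples in the SAP's exploratory section. Those are PCR-based gametocyte samples, not drug concentrations.
- A reader might expect a larger error in Part C children than in adults. No Part C PK schedule is visible, and the supplied protocol enrols only patients aged 12 and over.
- A reader might see a contradiction in fitting T1/2 on the log scale while integrating linearly. The terminal slope is a log-linear regression under any trapezoidal option, so nothing is contradicted.

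**Conclusion.** The point holds in conditional form. The protocol specifies the plain linear rule, and that rule overstates each exponentially declining interval by a known amount. Whether this matters for AUClast, AUC0-168h, AUCinf and CL/F depends on spacing relative to half-life, and both are redacted. On the assumptions above, the AUC excess is roughly 1-2% with dense sampling and up to about 10% on a complete but sparse grid. It is larger if a mid-profile sample is missed: AUC0-168h is 1.7% to 22.9% too high without the 72 h sample. The net sign can reverse if the peak is poorly sampled, so a flat statement that the trial's AUC is biased upward would go too far. PCT and PCR-corrected ACPR are untouched. This is an inexpensive improvement in method, not an error or inconsistency.

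**What to change.** In Protocol 8.7, replace the sentence on the linear rule with: *AUC will be calculated with the linear-up/log-down trapezoidal rule.* State the same rule in SAP 2.8, so that it does not depend on which protocol version is in force. Where comparison with earlier studies matters, list the linear AUC in a second column.

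The cost is one WinNonlin setting and one sentence in each document. AUC values will be slightly lower than under the linear rule, by a few percent if sampling is sparse, and the method will differ from any earlier study that used the linear rule; the second column covers that. The change does not repair a poorly sampled peak, which is a matter for the sampling schedule.
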